### **3.1 Safety Run-in and DLT Assessment**

This study will start with a safety run-in period. The first 3 participants will be sequentially enrolled, with a mandatory waiting period of 21 to 28 days after the immediate prior patient's PVSRIPO treatment before the next patient receives PVSRIPO. The 21- to 28-day waiting period also applies after the third patient receives PVSRIPO, prior to PVSRIPO treatment of the fourth patient.

The DLT evaluation period for the first 3 patients will begin once a patient who received PVSRIPO receives the first dose of pembrolizumab and continue for 21 days ( $\pm$  3 days to

account for variations in patient visit scheduling, weekends, etc.) after this first dose of pembrolizumab. This wait period allows sufficient time for safety review prior to the next patient receiving their first dose of pembrolizumab. If  $\geq 2$  of the first 3 patients treated with PVSRIPO followed by 1 dose of pembrolizumab experience a DLT, accrual will be halted, and the treatment plan may be modified, or the study may be closed.

If no DLT occurs in the first 3 participants, the dosing regimen will continue as planned and an additional 27 participants will be enrolled to further characterize safety and anti-tumor activity of treatment with PVSRIPO plus pembrolizumab.

However, if only 1 patient experiences a DLT of the first 3 participants treated, an additional 3 participants will be enrolled (without a waiting period between participants) to undergo DLT evaluation. If  $\leq 33\%$  of participants (ie,  $\leq 2$  of 6 total) experience a DLT, the 24 remaining participants will be enrolled. If  $> 33\%$  of participants (ie,  $\geq 3$  of 6) experience a DLT, the study will be halted, and the treatment plan modified, or the study may be closed. After the DLT evaluation period, ongoing monitoring of TEAEs will occur on at least a monthly basis by the Sponsor safety review team and by the DSMB, as specified in the safety plan and applicable charter, respectively.

If one of the first 3 (or 6) participants accrued withdraws from the study during the DLT evaluation period for reasons unrelated to the occurrence of a DLT, the participant will be replaced for the purpose of the initial DLT assessment. For details regarding events and criteria for meeting the definition of a DLT, see [Section 7.4](#).

### **3.2      Delay in pembrolizumab administration for ongoing peritumoral or cerebral edema (or other TEAE/reasons)**

Peritumoral edema may be associated with PVSRIPO treatment and there is potential for the same after immune checkpoint inhibition. As such, the first planned dose of pembrolizumab (scheduled 2 weeks after PVSRIPO infusion) will be delayed by up to two additional weeks in participants with any ongoing  $\geq$  Grade 3 PTE or CE or  $\geq$  Grade 2 AEs related to PTE or CE following PVSRIPO infusion requiring active treatment, such as new or worsening neurologic signs and symptoms (eg, hemiparesis requiring  $\leq 4$  mg/day dexamethasone or seizure requiring anti-epileptics), until such events resolve to  $\leq$  Grade 1.

If such events have not resolved to  $\leq$  Grade 1 by 4 weeks post-PVSRIPO infusion, or the patient has not received pembrolizumab for any reason by 4 weeks post-PVSRIPO infusion, the participant will not receive pembrolizumab under this trial and will be replaced. If a participant requires  $> 4$  mg/day of dexamethasone or equivalent prior to the first dose of pembrolizumab, the

participant will not receive pembrolizumab under this trial and will also be replaced. These replaced participants will not be considered in the initial DLT assessment of the treatment with PVSRIPO and pembrolizumab.

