	
The study will begin with a safety lead-in for evaluation of dose-limiting toxicity (DLT) of the combination prior to full open enrollment. As such, the first 3 patients will be sequentially enrolled with a mandatory waiting period of 21 to 28 days after the immediate prior patient's PVSRIPO infusion to allow for DLT assessment. The DLT evaluation period will begin once a patient receives PVSRIPO followed by the first dose of pembrolizumab and continue for 21 days after the first dose of pembrolizumab (<math>\pm</math> 3 days to account for weekends, patient visit scheduling issues, etc.). The initial DLT assessment will be based on the first 3 patients, which may be expanded up to 6 patients if any DLT are noted in the first 3 (see Sections 3 and 7.4 for additional detail regarding DLT assessment).
 
The first planned dose of pembrolizumab at Week 2 will be delayed by up to 2 additional weeks in patients with any ongoing <math>\geq</math> Grade 3 peritumoral edema (PTE) or cerebral edema (CE) or <math>\geq</math> Grade 2 AEs related to PTE or CE following PVSRIPO infusion or signs or symptoms related to these events that require active treatment (eg, treatment-emergent or worsening events such as hemiparesis requiring <math>\leq</math> 4 mg/day dexamethasone or seizure requiring anti-epileptics; see Section 5.7.2), until such events resolve to <math>\leq</math> Grade 1. If such events have not resolved to <math>\leq</math> Grade 1 by Week 4 post-PVSRIPO infusion, the patient will not receive pembrolizumab under this trial and will be replaced. Pembrolizumab may be administered any time between Weeks 2 and 4 once events resolve as outlined above, as applicable. The first planned pembrolizumab treatment may also be delayed for administrative or other reasons, including other TEAE that in the Investigator's opinion warrants delayed pembrolizumab treatment, but the first pembrolizumab treatment must occur by Week 4 post-PVSRIPO infusion, as noted above.
 
In addition, if a patient requires <math>></math> 4 mg/day of dexamethasone or equivalent prior to the first dose of pembrolizumab, the patient will not receive pembrolizumab under this trial and will be replaced. These replaced patients will not be considered in the initial DLT assessment of the combination but will be eligible for additional follow-up in this study and will be summarized separately from those receiving the combination. Their information may be utilized in exploratory comparative summaries relative to patients treated with PVSRIPO and <math>\geq</math> 1 dose of pembrolizumab in this study.
 
If <math>\leq</math> 33% of the initial participants in the safety lead in (<math>\leq</math> 1 of 3 or if <math>></math> 1 patient of the first 3 experiences a DLT and 3 additional patients are included for DLT assessment, <math>\leq</math> 2 of 6 patients) experience a DLT, the twenty-four remaining participants will be enrolled. If <math>></math> 33% of participants (ie, <math>\geq</math> 3 of 6) experience a DLT, the study will be halted, and the treatment plan modified, or the study may be closed. After the DLT evaluation period and the study is open to full enrollment, ongoing monitoring of TEAEs will occur on at least a monthly basis.

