**Planned Treatment:**

- Pembrolizumab (200 mg IV infusion)

**5.3.1      Delayed 1st Pembrolizumab Treatment: Week 3 to 4 visit (if needed) and Shift in Schedule of Assessments (Unscheduled Visit)**

Note: If the 1st pembrolizumab infusion is delayed from Week 2 (Visit 5) due to ongoing AE, etc., the schedule of assessments (days, weeks) shifts accordingly so the next planned visit would occur 3 weeks after the date of 1st pembrolizumab infusion. For example, if a patient's 1st treatment with pembrolizumab occurs at Week 3 (Study Day 21), their next scheduled clinic visit would be Week 6 (Study Day 42).

The Week 3 to Week 4 visit is only required if the first planned dose of pembrolizumab is delayed from Week 2.

The first pembrolizumab treatment is planned for Day 14 (2 weeks after PVSRIPO infusion); however, pembrolizumab treatment will be delayed by up to two additional weeks post-PVSRIPO infusion in patients with any ongoing  $\geq$  Grade 3 PTE or CE or  $\geq$  Grade 2 AEs related to PTE or CE following PVSRIPO infusion or for any related events requiring active treatment (eg, TEAE such as new or worsening neurologic signs and symptoms like hemiparesis requiring  $\leq$  4 mg/day dexamethasone or seizure requiring anti-epileptics), until such events resolve to  $\leq$  Grade 1. If such events have not resolved to  $\leq$  Grade 1 within 28 days (4 weeks) post-PVSRIPO infusion, the patient will not receive pembrolizumab under this trial and will be replaced.

The first pembrolizumab treatment may also be delayed by up to two additional weeks post-PVSRIPO infusion for administrative or other reasons, including other TEAE that in the Investigator's opinion warrants delayed pembrolizumab treatment, but the 1st planned treatment should occur as close to Day 14 as possible.

If the first pembrolizumab treatment is delayed for any reason, it may be given anytime between Weeks 2 through 4 so long as the event(s) leading to the delay have resolved as noted above.

There is a  $\pm$  7-day visit window for study visits after the first week of the study to account for these adjustments and to align future doses of pembrolizumab with the study visits and assessments.

Patients requiring  $> 4$  mg/day of dexamethasone or equivalent prior to the first dose of pembrolizumab will not receive pembrolizumab under this trial.

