**7.4 Assessment and Definition of Dose Limiting Toxicity**

For this study, assessment of treatment emergent DLT will occur after a patient receives PVSRIFO and until 21 days ( $\pm$  3 days) after the first dose of pembrolizumab.

Peritumoral and CE occur frequently in rGBM and may be secondary to the disease process itself, surgical procedures, necrosis from previous radiation, or inflammation due to immune infiltration of the brain or destruction of tumor cells, which may manifest as neurologic dysfunction. Given that transient PTE has been observed following PVSRIFO use, the primary focus for DLT will be neurologic events meeting the criteria for a DLT defined as follows:

1.  $\geq$  Grade 3 neurologic events related to PTE or CE within the first 3 weeks of the first pembrolizumab administration that:
  - a. Do not resolve to  $\leq$  Grade 1 with the management practices outlined herein ( $\leq$  4mg/dexamethasone or 7.5 mg/kg bevacizumab) within 3 weeks of initiating such treatments,

and/or

- b. Require surgical debulking of the PVSRIFO infused tumor within 3 weeks of the first pembrolizumab administration

**To assess for any other potential DLT, CTCAE v5.0 will be utilized, and the following will also be considered DLT if treatment related:**

1. Any of the following SAEs:
  - a. Treatment-related death
  - b. Treatment-related life-threatening event
  - c. A medically significant condition (defined as an event that compromises patient safety or may require medical or surgical intervention to prevent one of the outcomes above).
  - d. Requires inpatient hospitalization or prolongation of existing hospitalization
  - e. Results in persistent or significant incapacity or substantial disruption to conduct normal life functions
2. Any Grade 4 non-hematologic toxicity
3. Any Grade 3 non-laboratory-based toxicity that is not reversible to its pre-PVSRIPO treatment baseline within 2 weeks of onset with the following exceptions:
  - a. Grade 3 fatigue lasting  $\leq$  3 days or Grade 3 fatigue in a participant with Grade 1 fatigue at baseline
  - b. Grade 3 diarrhea, nausea, or vomiting without use of anti-emetics or anti-diarrheals per standard of care
  - c. Grade 3 adrenal insufficiency due to suboptimal steroid replacement therapy
  - d. Grade 3 rash without use of corticosteroids or anti-inflammatory agents per standard of care

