SAEs considered related the local inflammatory effect on the tumor (ie, peritumoral edema) should be reported in a way that distinguishes it from a more generalized brain edema (eg, "edema cerebral (peritumoral)". In cases where the edema is more generalized, reporting as "edema cerebral" would be more appropriate. In each case, the appropriate severity grade of the PTE or CE and the resulting symptoms/specific dysfunction should be noted in the edema-specific AE/SAE collection forms (and narrative description for SAE related to PTE or CE) by severity grade along with other relevant information (eg, start and stop date of each sign/symptom and any other information considered relevant by the investigator). Any signs or symptoms considered to be out of proportion to the extent of the PTE may be reported as additional SAEs, if indicated.

Except in cases of imminent life-threatening emergency, investigators should consult with the Sponsor Medical Monitor or designee is recommended prior to implementing anti-tumor treatments beyond the protocol-recommended supportive care options.

Delays and or discontinuation of pembrolizumab treatment should occur as outlined in **Sections 5.3** and **7.5.3** for events related to PTE and CE.

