### **7.5.3 Adverse Events of Immunologic Etiology Associated with Pembrolizumab**

Adverse events of an immunologic etiology have been associated with pembrolizumab exposure. These irAE may occur shortly after the first dose or several months after the last dose of pembrolizumab treatment and may affect more than one body system simultaneously. Therefore, early recognition and initiation of treatment is critical to reduce complications. Existing clinical trial data have shown that most irAEs related to pembrolizumab were reversible and could be managed with interruptions of pembrolizumab, administration of corticosteroids, and/or other supportive care. See **Section 6.5.4.3** on medication use for treatment of irAE.

Depending on the severity of the irAE, pembrolizumab will be temporarily withheld or permanently discontinued. In general, for an irAE requiring dose interruptions, low-dose dexamethasone ( $\leq 4\text{mg/day}$ ) should be initiated and tapered when the irAE is  $\leq$  Grade 1.

For a life-threatening irAE, IV dexamethasone should be initiated first followed by oral steroids. Other immunosuppressive treatment should also be initiated if the irAEs cannot be controlled by corticosteroids alone.

The next doses(s) of pembrolizumab will be withheld until the irAE has been reduced to  $\leq$  Grade 1 and dexamethasone dose has been tapered to  $\leq$  4mg/day and/or discontinued.

Pembrolizumab should be permanently discontinued if the irAE does not resolve within 12 weeks of last dose or dexamethasone cannot be reduced to  $\leq$  4 mg/day within 12 weeks.

- With regard to events  $\geq$  Grade 2 related to PTE or CE (eg, hemiparesis, seizure), pembrolizumab treatment should be held until those events resolve to  $\leq$  Grade 1. Pembrolizumab should be permanently discontinued for Grade 4 PTE or CE and/or events  $\geq$  Grade 3 related to PTE or CE.

**Refer to the most recent Keytruda® (pembrolizumab) package insert and “Guide for Keytruda®” for a list of adverse reactions for which pembrolizumab should be interrupted or permanently discontinued along with recommended management. This may include but not be limited to the following:**

- Immune-mediated pneumonitis: Withhold for moderate, and permanently discontinue for severe, life-threatening or recurrent moderate pneumonitis.
- Immune-mediated colitis: Withhold for moderate or severe, and permanently discontinue for life-threatening colitis.

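### Protocol Section 3.2 delays the first pembrolizumab dose for a Grade 2 or higher edema-related event only if it needs active treatment; 5.3.1 and the other statements of the rule require the hold regardless

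*Protocol*

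**What the plan says.** The rule for holding pembrolizumab because of edema appears in four places in the Protocol. In the quotes, the grade is preceded by a greater-or-equal sign that falls outside the quoted words.

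- **Section 3.2**, the section titled for this decision: delay for ongoing PTE/CE of Grade 3 or higher, or for "Grade 2 AEs related to PTE or CE following PVSRIPO infusion requiring active treatment, such as new or worsening neurologic signs and symptoms".
- **Section 5.3.1**, in the visit instructions: delay for ongoing PTE/CE of Grade 3 or higher, or for "Grade 2 AEs related to PTE or CE following PVSRIPO infusion or for any related events requiring active treatment".
- **Synopsis, Study Design**: the same two graded triggers, then "or signs or symptoms related to these events that require active treatment".
- **Section 7.5.3**, under immune-related events with pembrolizumab: for events at or above "Grade 2 related to PTE or CE (eg, hemiparesis, seizure), pembrolizumab treatment should be held until those events resolve to" Grade 1 or lower. No treatment condition is attached.

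Section 7.5.2 adds a pointer for PTE/CE: "Delays and or discontinuation of pembrolizumab treatment should occur as outlined in" Sections 5.3 and 7.5.3. It does not name 3.2. The SAP does not restate the rule.

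Sections 3.2 and 5.3.1 both set the release condition at Grade 1 or lower, and both replace a patient whose qualifying event has not resolved by four weeks after PVSRIPO.

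**The concern.** This rule is the safety gate for starting a checkpoint inhibitor in a patient who may still have virus-induced edema. Section 3.2 itself notes that checkpoint inhibition may also cause edema. The leading DLT definition in Section 7.4 concerns "neurologic events related to PTE or CE within the first 3 weeks of the first pembrolizumab administration that" fail to resolve with the recommended management or require debulking. The condition that should hold the first dose and the toxicity that the lead-in looks for are therefore closely linked.

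If two sections give different triggers, two sites can treat the same patient differently. One site may dose while the other holds. If the event persists to the four-week limit, the holding site must replace the patient, who is then outside the initial DLT assessment (Section 3.2), the combination datasets (Section 4.5) and the primary efficacy set (Protocol 8.4.6; SAP 4.1). The lead-in starts with 3 patients and may extend to 6, so even one such patient counts there.

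**Working it through.** No sample-size or power figure is involved. The check is a comparison of wording, followed by the timing arithmetic.

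**Step 1. Parse the triggers.** In 3.2 the treatment phrase directly follows the graded adverse events and restricts them. In 5.3.1 the words between the graded events and the treatment phrase begin with *or*. The graded event therefore stands alone, and a related event needing treatment is a third, separate trigger. The Synopsis has the same *or* structure, although its treatment clause could be read as covering the whole list. Its cross-reference for this point is to Section 5.7.2, Radiographic Imaging, which does not settle the matter. Section 7.5.3 has no treatment condition.

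**Step 2. Apply both sections at Day 14.**

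| State at Day 14 | 3.2 | 5.3.1 |
|---|---|---|
| PTE/CE Grade 3 or higher | delay | delay |
| Related event Grade 2 or higher, needing treatment | delay | delay |
| Related event Grade 2 or higher, no treatment needed, PTE/CE below Grade 3 | no mandatory delay | delay |

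Only the third row differs. If the treatment phrase in 3.2 is taken to cover the Grade 3 PTE/CE trigger as well, the third-row conflict remains.

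**Step 3. Timing.** Planned first dose is Day 14 and the limit is Day 28, a difference of 28 − 14 = 14 days. The DLT window ends 21 days (±3) after the first dose:

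- first dose on Day 14: 14 + 21 = Day 35 (32 to 38);
- first dose on Day 28: 28 + 21 = Day 49 (46 to 52).

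This shift is not specific to the conflict. Section 5.3.1 already allows a delay of up to two further weeks for administrative or other reasons, and note 18 of Protocol Table 1 allows the first dose up to Day 28.

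**Step 4. What is specific to the conflict.** Take the third-row patient.

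- *Before Day 28:* 5.3.1 forbids the dose while the event is Grade 2 or higher. Section 3.2 does not require a hold.
- *At Day 28, still unresolved:* under 5.3.1 the patient gets no pembrolizumab in the trial and is replaced. Under 3.2 the event was never a qualifying one, so a patient already dosed stays in the DLT and primary efficacy sets.

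**Step 5. How many.** The documents give no figure from which the number of third-row patients can be derived. The notice on immunoprogression and Section 6.5.4 recommend treatment for symptomatic edema, which moves most such patients to the second row. Treatment is at the investigator's discretion, so the third row is not empty by design.

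**The case against.** The strongest reply is that the Protocol already shows which text operates. Section 7.5.2 points to 5.3 and 7.5.3, and Section 5.3 holds the instructions used on the dosing day. The Synopsis agrees on its natural reading. Holding satisfies every section, and 3.2 never orders a dose. Harm therefore needs a site that reads 3.2 alone. All of this stands. It shows that the stricter rule is intended and keeps the point modest, but it does not correct the sentence in the section named for the decision. The power to delay for other events is optional, so it does not supply the missing requirement.

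A reader might infer more than the documents support:

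- *That the conflict moves the first dose and the DLT window by 14 days.* That range is already open to any patient for other reasons. The start of the window is also not a firm basis: Section 3.1 says "The DLT evaluation period for the first 3 patients will begin once a patient who received PVSRIPO receives the first dose of pembrolizumab", while 7.4 counts from PVSRIPO. Both end it 21 days after the first dose.
- *That dosing such a patient is a major deviation under Protocol 8.4.6.* The relevant item concerns continuing treatment after withholding criteria are met, and stretching it to a first dose is doubtful. The list serves the per-protocol analysis, which SAP Section 6 drops in any case.
- *That the trial's size or power is affected.* It is not.

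It is also fair to say that SAP Section 6 reports that the full sample was not enrolled. This suggests that few or no first doses may remain for a correction to guide.

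**Conclusion.** The inconsistency is real. Section 3.2 makes the mandatory delay for Grade 2 or higher edema-related events depend on active treatment; 5.3.1, the Synopsis on its natural reading and 7.5.3 do not. The firm contrast is 3.2 against 5.3.1, because the Synopsis admits a second reading and 7.5.3 sits under immune-related events.

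Its reach is one patient state: an ongoing, untreated edema-related event of Grade 2 or higher with PTE/CE below Grade 3. It has two specific consequences: possible dosing during ongoing edema, and different replacement of patients unresolved at Day 28, hence different membership of the DLT and primary efficacy sets. The number affected is unknown. That it is small is a judgement resting on the treatment recommendations, not on data. The point should be fixed because it concerns a safety rule and the correction is simple, not because a large effect on results can be shown.

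**What to change.** Replace the trigger in 3.2 with the full trigger of 5.3.1, and use the same sentence in the Synopsis. Delay the first dose for any of the following, until Grade 1 or lower, with the Day 28 limit unchanged:

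1. ongoing PTE/CE of Grade 3 or higher;
2. an ongoing PTE/CE-related event of Grade 2 or higher, whether or not it is treated;
3. any related event requiring active treatment.

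The third item adds little, because a Grade 1 event already meets the release condition, but keeping it makes the sections identical.

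Do not carry the stopping rule of 7.5.3 into this gate. That section says "Pembrolizumab should be permanently discontinued for Grade 4 PTE or CE and/or events" of Grade 3 or higher related to PTE/CE, whereas 3.2 and 5.3.1 delay such patients and allow dosing after resolution. Any change there should be a separate, explicit decision.

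The cost is a wording change made by protocol amendment, with the ethics approval that this needs. A few more patients may be held or replaced. No new procedures or data fields are required. If no first doses remain, the affected patients could instead be identified from the adverse event, medication and pembrolizumab infusion listings already planned in SAP Section 10.
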